Starting from **Visit 6/Week 24**, FFSG and FS A1C will be measured at scheduled and unscheduled site visits, and glycemic intensification will be initiated if the participant meets criteria (Table 4). Between site visits, participants with FFSG >130 mg/dL (7.2 mmol/L) at home for 3 consecutive days will come to the site for an **Unscheduled Visit** if, in the investigator's judgment, the participant has been compliant with study medication and diet/exercise recommendations. At the unscheduled site visit, the participant's FFSG and FS A1C will be measured, and the participant will initiate glycemic intensification if both values meet criteria (Table 4). If the participant is on metformin alone, insulin glargine will be initiated (dose at the investigator's discretion based on accepted local, national or international guidelines). If the participant is on metformin + insulin the total daily insulin dose will be increased by ≥15% (Table 2).

 Participant's Background Therapy
 Phase A Rescue Therapy OR Phase B Intensification Therapy (for participants not rescued in Phase A)

 Metformin alone Metformin + Insulin
 Insulin glargine Increase insulin dose ≥15%

Table 2 Glycemic Rescue/Intensification Strategy

Note: In Phase A and Phase B, participants requiring transient (ie, <14 days) initiation of insulin or an increase in insulin (≥15% of the dose at baseline), for participants on background insulin therapy (eg, an intercurrent illness) will not be considered as having initiated rescue/intensification. Down-titration or weaning of insulin after a temporary initiation or increase in dose should occur at the investigator's discretion.

Note that participants rescued or intensified with basal insulin for 6 weeks or more, can have prandial insulin added at the investigator's discretion. The choice, dose, and titration of prandial insulin will be the investigator's responsibility.

Participants <18 years of age, who refuse to initiate insulin or up-titrate their background insulin (or for whom it is considered inappropriate) when glycemic thresholds for rescue/intensification are met will be discontinued from study medication (see Section 7.1). Participants ≥18 years of age can be rescued or undergo glycemic intensification using any of the antihyperglycemic agents approved for use with ertugliflozin.

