If a participant discontinues study medication in Phase A but agrees to continue in the study, the participant's diabetic care will be handled by the participant's primary diabetes doctor or the investigator outside of this protocol. The study-site personnel will only collect assessments specified in the SoA.

Telephone Call Week 18

The **Week 18 Visit** is a telephone call visit. The site will call the participant/participant's legally acceptable representative and will complete all procedures indicated in the SoA. All AEs, changes in concomitant medication, and any hypoglycemia events will be documented in the appropriate eCRFs.

8.10.5 Double-Blind Treatment Period – Phase B - Visit 6/Week 24 Through Visit 8/Week 54

The first dose of Phase B double-blind study treatment will be taken as a witnessed dose at the site *after* completion of all procedures for the Visit 6/Week 24 study visit. It is essential that all procedures be performed *before* the participant takes the witnessed dose.

Participants Who Have *Not* **Been Rescued During Phase A** will continue on their double – blind study treatment and will initiate glycemic intensification as outlined in Table 2 if their

FFSG is >130 mg/dL (7.2 mmol/L) and their FS A1C is >7.5% (58 mmol/mol) (Table 4, Section 6.5.1).

Participants Who Have Been Rescued During Phase A will continue on their double – blind study treatment and background medication of metformin + insulin (for rescue). Insulin doses will be titrated based on glycemic responses at the investigator's discretion.

If a participant discontinues study medication in Phase B but agrees to continue in the study, the participant's diabetic care will be handled by the participant's primary diabetes doctor or the investigator outside of this protocol. The study site will only collect the assessments specified in the SoA.

Telephone Call Week 30 and Week 44

Week 30 and Week 44 are telephone call visits. The site will call the participant/participant's legally acceptable representative and will complete all procedures indicated in the SoA. All AEs, changes in concomitant medication, and any hypoglycemia events will be documented in the appropriate eCRFs.

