9.6.1 Statistical Methods for Efficacy Analyses

This section describes the statistical methods that address the primary and secondary objectives. Methods related to exploratory objectives will be described in the sSAP.

There will be 2 estimands for the analysis of continuous efficacy endpoints, TP and TE. The primary hypothesis will be tested using both estimands. Based on local regulatory requirements, one of the estimands will be considered primary and the other supplementary. The key secondary endpoints and hypotheses associated with them (H2 and H3) will be analyzed under only the TP estimand.

The TP estimand consists of the following elements:

- Target population: Pediatric patients (age 10 to 17 years, inclusive) with T2DM who meet the glycemic criteria defined in this protocol
- Variable: Change from baseline in A1C at Week 24
- Intercurrent events: Regardless of whether study treatment or rescue medication was taken
- Population level-summary: Difference in means at Week 24
- Treatment Comparison of Interest: The effect of being randomized to ertugliflozin (combined doses) versus placebo.

Analyses corresponding to the TP estimand will include all available data at the Week 24 timepoint, including data after rescue or after the last dose of study treatment in any participants who remain in the study after discontinuing study treatment.

Analyses corresponding to the TP estimand will include all available data at the Week 24 timepoint, including data after rescue or after the last dose of study treatment in any participants who remain in the study after discontinuing study treatment.

The TE estimand consists of the following elements:

- Target population: Pediatric patients (age 10 to 17 years, inclusive) with T2DM who meet the glycemic criteria defined in this protocol
- Variable: Change from baseline in A1C at Week 24 as if all participants remained on treatment
- Intercurrent events: Data obtained after discontinuation of treatment or after taking rescue treatment are not relevant to this estimand
- Population level-summary: Difference in means at Week 24
- Treatment comparison of interest: The effect of taking the randomized treatments (ertugliflozin [combined doses] versus placebo).

The TE estimand will exclude measurements collected more than 5 days after the last dose of study treatment or after other AHA treatments, such as rescue/intensification treatment, are added.

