The RD analysis may not be feasible due to insufficient observed Week 24 data post discontinuation of study medication. If the number of RD participants per group is at least 50% of participants who discontinue from study medication per arm, then RD will be the primary approach to impute missing data for the TP estimand. If at least one group has either less than 50% RD participants or fewer than 5 total RD participants, then RD will not be performed, and WI will become the primary analysis method. If the minimum data requirement for the RD method is met, then WI will be implemented as a sensitivity approach for the TP estimand. The WI analysis assumes participants who prematurely discontinued from the study or who have an intermittent missing Week 24 value would have a 'washout' of any potential effect of the assigned study medication.

For all analyses involving simulated data, a seed of 8835059 will be used for random number generation.

A constrained longitudinal data analysis (cLDA) model, based on Liang and Zeger [Liang, K.-Y. and Zeger, S. L. 2000], will be used for analyses addressing the TE estimand for A1C mean change from baseline and FPG mean change from baseline. Time will be treated as a categorical variable so that no restriction is imposed on the trajectory of the means over time. The cLDA model will also adjust for treatment, the age stratum, the insulin use stratum, and the interaction of time by treatment. The cLDA model assumes a common mean across treatment groups at baseline within each age and insulin use category (due to randomization) but different means between categories, and a different mean for each treatment at each of the post-baseline timepoints. In the cLDA model, the response vector consists of baseline and the values observed at each post-baseline timepoint. The treatment difference in terms of mean change from baseline to a given timepoint will be estimated and tested from this model. An unstructured covariance matrix will be used to model the correlation among repeated measurements.

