For the cLDA model, the Kenward-Roger adjustment will be used with restricted (or residual) maximum likelihood (REML) to make proper statistical inference. An unstructured covariance matrix will be used to model the correlation among repeated measurements and hence avoids the potential bias that could result from the use of specific structured covariance models. If the unstructured covariance model fails to converge with the default Newton-Raphson algorithm, the Fisher scoring algorithm or other appropriate methods can be used to provide initial values of the covariance parameters. In the rare event that none of the above methods yield convergence, a structured covariance such as Toeplitz can be used to model the correlation among repeated measurements. In this case, the empirical option will be used because the sandwich variance estimator is asymptotically unbiased while the model-based variance estimator can substantially overestimate or underestimate the true variance. The cLDA model uses the maximum likelihood principle to estimate the parameters and account for missing data in an implicit fashion.

Although the baseline measurement is included in the response vector, it is independent of treatment, and hence, the baseline means are constrained to be the same for different treatment groups within the same age and insulin use categories. Of note, in the event that there are no missing data, the estimated treatment difference from the above cLDA model will be identical to that from a traditional longitudinal ANCOVA model, which uses the baseline value as a covariate. However, unlike longitudinal ANCOVA, the cLDA model accounts for variability in the baseline values, thus providing more accurate standard errors and CIs for individual treatment effects. Moreover, this model allows the inclusion of participants who are missing either the baseline or post-baseline measurements, thereby increasing efficiency.

The cLDA method assumes that the mechanism for missing data is missing at random (MAR).

Assessment of the Key Secondary Endpoints

The key secondary endpoints will be evaluated under only the TP estimand analysis approach.

PROTOCOL/AMENDMENT NO.: 059-04

All elements of the TP estimands below are the same as the primary TP estimand except for the treatment comparisons:

Treatment comparison of interest:

For H2 - The effect of being randomized to dose-optimized ertugliflozin versus placebo.

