- 1) Fit a regression model as $Y_{24} = \beta_0 + \beta_1 * Y_0 + \gamma * X + \text{error}$, where Y_0 and Y_{24} are the placebo group A1C values at Baseline and Week 24, respectively, and X is a matrix for the age and insulin stratum fixed covariates.
- 2) Impute missing Week 24 A1C values for ertugliflozin using the estimated mean from the above model and standard deviation equal to the RMSE from the model.

For participants in the placebo group:

- 1) Fit models according to the intermittent missing data pattern with A1C values from the placebo group only:
 - a. For participants with only Baseline data: $Y_{24} = \beta_0 + \beta_1 * Y_0 + \gamma * X + \text{error}$
 - b. For participants with only Baseline and Week 6 data: $Y_{24} = \beta_0 + \beta_1 * Y_0 + \beta_2 * Y_6 + \gamma * X + \text{error}$
 - c. For participants with only Baseline, Week 6 and Week 12 data: $Y_{24} = \beta_0 + \beta_1 * Y_0 + \beta_2 * Y_6 + \beta_2 * Y_{12} + \gamma * X + error$
- 2) Impute missing Week 24 A1C values for placebo using one of the 3 models above based on the missing data pattern with a mean equal to the mean from the regression model and a standard deviation equal to the RMSE from the model.

Descriptive statistics will be used to summarize the A1C mean change from baseline at Week 24 for the individual ertugliflozin dose arms in the subset of participants who were rerandomized at Visit 5/Week 12. All other continuous efficacy endpoints with the exception

of the 2 key secondary endpoints associated with hypotheses H2 and H3, including the Week 12 A1C change from baseline, will be analyzed following the same cLDA method used for the A1C TE estimand under H1 (combined ertugliflozin doses vs. placebo) and will not be analyzed under the TP estimand.

Week 54

The Week 54 analyses will be based on the same FAS population used for the Week 24 analyses. The statistical models for the analyses at Week 54 will be analogous to those at Week 24, except that no between-group comparisons will be provided for **Week 54**. The efficacy endpoints will be summarized for within-group mean change from baseline with estimates and 95% CIs calculated from the analysis model.

Table 7 summarizes the analysis strategy for primary and secondary efficacy endpoints at Week 24 and at Week 54.

Table 7 Analysis Strategy for Efficacy Variables at Week 24 and at Week 54

Variable	Estimand/Approach	Statistical Method	Missing Data Approach
Primary			

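### Week 54 FPG: A1C and interim fasting glucose decide who is censored but are not in the FPG model, so missing-at-random is doubtful and the within-group change is likely too favourable

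*Combined protocol and SAP*

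**What the plan says.** **Trigger.** For participants not rescued in Phase A, Section 6.5.1 provides, from Week 24 on, that "FFSG and FS A1C will be measured at scheduled and unscheduled site visits, and glycemic intensification will be initiated if the participant meets criteria". There is also a second route: "Between site visits, participants with FFSG >130 mg/dL (7.2 mmol/L) at home for 3 consecutive days will come to the site", provided they are judged compliant. At that unscheduled visit "the participant will initiate glycemic intensification if both values meet criteria". Section 8.10.5 repeats the two thresholds of Table 4: "FFSG is >130 mg/dL (7.2 mmol/L) and their FS A1C is >7.5% (58 mmol/mol").

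**Censoring.** Under the TE estimand (Section 9.6.1), measurements are excluded "after other AHA treatments, such as rescue/intensification treatment, are added". Table 7 gives FPG a single analysis, TE by cLDA with model-based handling of missing data, and Section 9.6.1 rules out a TP analysis for it.

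**Model.** "In the cLDA model, the response vector consists of baseline and the values observed at each post-baseline timepoint". The other terms are treatment, time, their interaction, and the age and insulin strata. "The cLDA method assumes that the mechanism for missing data is missing at random (MAR").

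**Week 54.** The models are analogous to those at Week 24, without between-group comparisons. "The efficacy endpoints will be summarized for within-group mean change from baseline with estimates and 95% CIs calculated from the analysis model". Section 3 lists the within-group FPG change at 54 weeks as a secondary objective. Table 14 (Appendix 11) has two post-baseline FPG windows: any Phase A value from Day 2 is Week 24, and any Phase B value from Day 1 is Week 54. The visible text gives no sensitivity analysis for Week 54 FPG.

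**The concern.** A likelihood model for FPG is valid under missing-at-random only if, given the FPG values it contains, being censored tells us nothing more about Week 54 FPG. Here it probably does. Two participants with the same baseline and Week 24 FPG can part ways because one has A1C above 7.5%, or because fasting glucose rises at Week 30, 38 or 44. The one with worse glycemia is censored; the other stays and supplies the Week 54 regression. The model then predicts the censored participants from a better-controlled subset.

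At stake is a stated secondary estimate with its 95% CI. The interval would be centred too low, and nothing in the planned output would show it.

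**Working it through.** **1. The plan's own figures.** None is given for Week 54 FPG: no mean, SD, correlation, intensification rate or expected placebo drift. The nearest stated figure is the TE power for Week 24 A1C (Section 9.9). It reproduces: 0.86 x 110 = 94.6 and 0.86 x 55 = 47.3; with 95 versus 47, difference 0.75, SD 1.5 and two-sided 0.05 (assumed), power is 0.8006. It says nothing about the size of this bias.

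**2. The planned estimator.** Apart from strata, the cLDA with unstructured covariance is equivalent to two regressions:
- Y24 on arm and Y0, among those observed at Week 24;
- Y54 on arm, Y0 and Y24, among those observed at Week 54.

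The Week 54 change is E[Y54 | arm, mean Y0, predicted Y24] minus the common baseline mean. It is unbiased if E[Y54 | Y0, Y24, arm] is the same in censored and uncensored participants. Censoring occurs when FFSG(t) > 130 and A1C(t) > 7.5 at some t from Week 24 on. If A1C(t) or FFSG(t) predicts Y54 beyond Y0 and Y24, the uncensored mean is the lower one.

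**3. Main simulation (set A, placebo).** Thresholds are from Tables 3 and 4 and the screening A1C range from Section 5.1. Everything else is assumed: mean FPG 140-155 mg/dL; stable between-person SD 20-35; slow within-person SD 12-22; daily SD 12-22; mean A1C 7.7-8.2%; A1C variation independent of glucose SD 0.3-0.7; 40-80% of triggers acted on. That is 128 settings at each true placebo drift of 0, 5, 10 and 20 mg/dL.

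| Rule simulated | Median bias by drift (mg/dL) | Range |
|---|---|---|
| Full rules, later FPG missing | -7.9, -7.8, -9.0, -9.8 | -25.2 to -3.1 |
| Same, A1C removed from trigger | -8.1, -7.9, -8.5, -9.2 | -29.1 to -2.0 |
| Week 24 A1C criterion alone | -0.7, -0.6, -0.6, -0.6 | -4.6 to +0.5 |
| Full rules, baseline and Week 24 A1C added to model | -6.2, -6.6, -7.1, -8.1 | -23.0 to -2.1 |
| Full rules, intensification-visit FPG counted as Week 54 | +1.3, +0.5, -0.6, -3.4 | -8.6 to +6.3 |

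As a control, censoring on observed Week 24 FPG alone gave a bias of about 0 (-0.5). Under the full rules 45-94% of placebo had no Week 54 value. A harsher variant without a stable person effect gave -12 to -49 under the full rules.

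Rows 1 to 3 show that interim fasting glucose, not the A1C criterion by itself, is the main driver in this grid.

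**4. Which information repairs it.** Two further sets, both with placebo drift of about +8 mg/dL, give these median placebo biases:

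| Set and trigger route | Planned model | + baseline and Week 24 A1C | + Week 38 glycemia |
|---|---|---|---|
| B (128 settings), scheduled visits | -3.6 | -2.2 | -0.3 |
| B, home FFSG added | -19 | not given | about -15 |
| C (32 settings), scheduled visits | -16 | -12.5 | about 0 |
| C, home FFSG triggers | -18 | not given | -9 |

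In set B the ertugliflozin medians under the planned model were -3.0 and -13. The planned model was low in every setting of both sets. For the same scheduled-visit rule, however, the median was -3.6 in one and -16 in the other: the size follows the assumed inputs.

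**5. Table 14.** In a separate simulation of 110 and 55 participants with triggers at Weeks 24 and 38 only, the base-case biases were -27.0 - (-7.6) = -19.4 on ertugliflozin and -17.6 - 7.6 = -25.2 on placebo. Letting a pre-intensification Week 38 FPG stand as Week 54 changed them to -15.8 - (-7.6) = -8.2 and -3.7 - 7.6 = -11.3. In set B the same step left a median placebo bias of -0.2 (range -4.8 to +3.1) with scheduled triggers, but -12 with home triggers.

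**The case against.** The strongest reply is Table 14. Read literally, it places any Phase B FPG in the Week 54 window. Section 8.10.7 requires fasting laboratory tests at the Rescue Visit, and Appendix 2 restricts only A1C at early rescue or intensification visits. If FPG is drawn there, a pre-insulin value represents many intensified participants, and in set A the bias nearly vanishes or changes sign. This stands in part. The schedule of activities is blacked out, so the draw cannot be confirmed. Those intensified at Visit 6 would have only their Week 24 value. And an earlier reading labelled Week 54 is a different quantity, not a remedy.

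Not everyone above the thresholds is censored: Section 6.5.1 asks for at least 80% compliance first, and insulin for under 14 days does not count. This lowers the intensification rate but does not make censoring independent of later glucose.

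The consequence is limited: Week 54 is within-group, with no hypothesis and no planned contrast. That is correct.

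A reader might infer that the defect is simply the missing A1C term and that adding A1C cures it. The simulations do not support that: the Week 24 A1C criterion alone gave about -0.6 mg/dL in set A, and adding baseline and Week 24 A1C left most of the bias.

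A reader might also infer that placebo will appear to improve. In set A under the full rules, a true worsening appeared as improvement in 87% of settings at +5 drift, 45% at +10 and 9% at +20. The harsher variant gave 99-100% at +10 and +20. With the Table 14 mapping it was 0-4% in set A and up to 36% in the harsher variant. The documents supply none of the inputs that would decide between these.

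**Conclusion.** The point holds, with limits. The text shows that A1C and fasting glucose from Week 24 on determine who loses a Week 54 FPG value, and that the FPG model contains neither A1C nor any interim glucose. Missing-at-random is therefore doubtful by design. If FPG after intensification is treated as missing, the likely direction is low, that is too favourable, in both arms; under some assumptions a true placebo worsening can appear as an improvement.

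The size cannot be fixed from the documents. Plausible assumed inputs gave placebo biases from a few mg/dL to more than 20, and the unsettled Table 14 mapping can shrink or reverse them. The direction rests on A1C or interim glucose predicting later FPG beyond the modelled values, which is likely but is not a figure in the plan.

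The Week 24 primary and key secondary tests are unaffected. This is worth amending for a stated secondary estimate; it does not threaten the confirmatory conclusions.

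**What to change.** In Section 9.6.1 (Week 54), Table 7 and Table 14:

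1. Estimate Week 54 FPG by multiple imputation or a joint A1C and FPG model that uses A1C and FPG/FFSG at baseline, Week 24, Week 38 and any recorded intensification visit. Baseline and Week 24 A1C alone are not enough.
2. State that a pre-intensification Phase B FPG does not stand as the Week 54 value, and use it as an interim value in that model.
3. Add a delta-adjusted sensitivity analysis, because home-FFSG triggers leave residual bias even with Week 38 data (medians of -9 and about -15 mg/dL in the two sets above).
4. Report the number of non-censored Week 54 values per arm and, beside the model estimate, the observed Week 54 change regardless of intensification.

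The cost is SAP text and more programming. The interval will be somewhat wider (about 10-20% in the 110/55 simulation), and the estimate still relies on extrapolation above the Table 4 thresholds. Central and site A1C at Week 38 are specified (Appendix 2), and FFSG is measured at Phase B site visits (Section 6.5.1). Whether FPG is drawn at Week 38 or at intensification visits should be confirmed against the schedule of activities before the model is written.
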